Patients will be randomly assigned by a research assistant, by using a computer-generated randomization sequence to undergo colonoscopy with either inspection and polypectomy during both insertion and withdrawal of colonoscope (study group) or inspection and polypectomy entirely during withdrawal of colonoscope (control group). Randomization will be done via concealed allocation with a sealed envelope that designate study group or control group. The colonoscopist is not blinded to group assessment.

Procedure

Colonoscopies will be performed by two experienced colonoscopists by using a standard colonoscopy (CF-Q260AI or CF-Q260AL; Olympus Medical Systems Corp., Tokyo, Japan). All procedures are performed under moderate conscious sedation with fentanyl (United Biomedical, Taipei, Taiwan) and midazolam (Dormicum; Roche Pharmaceuticals, Basel, Switzerland) according to the current guidelines [24]. Carbon dioxide insufflation is used for all endoscopic procedures. All patients receive 3-L polyethylene glycol (PEG; Klean-Prep, Helsinn Birex Pharmaceuticals Ltd., Dublin, Ireland) for bowel preparation. A split-dose of the PEG preparation is provided for morning colonoscopy (2 L consumed in the evening before the colonoscopy and 1 L consumed in the early morning of the colonoscopy) and a same-day preparation is provided for the afternoon colonoscopy. The level of colon cleansing is prospectively evaluated with the BBPS score after all cleansing maneuvers are completed.

For patients in the study group, the colonic lumen is washed with saline and the fluid and debris are suctioned as the instrument is slowly inserted from rectum to cecum. Deliberate and systematic inspection of the colonic mucosa is performed with adequate luminal insufflations during both the insertion and withdrawal phases. Polyp size is determined by comparison with open colonoscopic biopsy forceps pushed against the polyp or, in some cases of pedunculated polyp by direct measurement after retrieval. Polyps with size $<10\text{mm}$ are removed as they are identified on insertion and withdrawal. Polyps with size $\geq10\text{mm}$ are removed only

during withdrawal.

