For patients in the control group, deliberate mucosal inspection and polyp removal are performed exclusively on instrument withdrawal. During insertion, minimal mucosal inspection and insufflation are applied to efficiently advance the instrument into cecum. If a polyp is found during insertion, endoscopists are instructed to make a mental note of it and find it during withdrawal for polypectomy.

Definition

Complete colonoscopy is defined as reaching and taking pictures of the cecum and ileocecal valve. Insertion time is defined as the time between the scope insertion and cecal intubation, including the time taken for mucosal clearing and polypectomy. Withdrawal time is defined as the duration between the time at which the cecum is reached and the time at which the scope is withdrawn from the anus, including the time taken for mucosal clearing and polypectomy. Total procedure time is the sum of insertion time and withdrawal time. The quality of bowel preparation is classified as excellent (BBPS score of 8 or higher), good (BBPS score of 7), or fair (BBPS score of 6).

The location of colorectal polyps is defined according to the anatomical distribution. The portion of the colon above the level of the splenic flexure is defined as the proximal colon. Diminutive polyp is defined for polyp with size $\leq 5\text{mm}$. Small polyp is defined for polyp with size 6-9mm. Large polyp is defined for polyp with size $\geq 10\text{mm}$. Adenomas include all adenomas and sessile serrated adenoma. Advanced adenoma is defined as those lesions with one of the following criteria: 1) lesions larger than 10 mm in diameter; 2) lesions with a villous component; 3) lesions with high-grade dysplasia; and 4) lesions with invasive features. ADR is defined as the proportion of colonoscopies where at least one adenoma is found. Advanced ADR is defined as the proportion of colonoscopies where at least one advanced adenoma is found. PR is defined as the proportion of patients undergoing colonoscopy in whom at least one polyp is removed. MAP is defined as the total number of adenomas detected divided by the number of colonoscopies. MAP+ is defined as the total number of adenoma detected divided by the number of colonoscopies in which at least one adenoma is found. ADR-Plus is defined as the mean number of adenomas detected after the first adenoma in procedures in which at least one adenoma is found. PSP-DR is defined as the proportion of patients undergoing colonoscopy in

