whom at least one serrated polyp (hyperplastic polyp, sessile serrated adenoma/polyp, traditional serrated adenoma) is identified proximal to the splenic flexure. The mean neoplastic polyp detection rate (MNP-DR) is defined as the total number of adenomas plus proximal serrated polyps (hyperplastic polyp, sessile serrated polyp) divided by the number of colonoscopies.

The grade of the colonoscopy difficulty is rated by the endoscopist using a 10-point Likert scale: 1, being extremely easy; and 10, being extremely difficult. Distraction during withdrawal phase is determined by the time of mucosal clearing and suction divided by the total withdrawal time and the total water volume required for mucosal clearing. Patient's subjective assessment of discomfort during the procedure is graded by patients with a 10-cm visual scale: 0, being no pain; and 10: being extremely severe pain.

Statistical analysis

The primary aim of the study is to evaluate whether there is a difference in the ADR between the two study groups. We calculate the required sample size by using the assumption of a 40% ADR in the control group [25]. For the study to have 85% power to detect a 15% increase in ADR with a 5% significance level, the study needs 211 participants per group to achieve significance (two sided). To account for dropouts, incomplete procedures, and inadequate preparation, an additional 10% will be enrolled. Therefore a total of 464 patients (232 in each group will be enrolled. Summary statistics are presented as frequencies and percentages in the case of categorical variables and as the means with standard deviations in the case of continuous variables. Student's t tests for continuous factors, Wilcoxon rank sum tests for ordinal variables (such as polyp size), and Chi-square tests for categorical variable are uses to assess differences in demographic and clinical characteristics of patients in each group. All calculations are conducted using SAS version 9.3 or later (SAS Institute Inc., Cary, NC, USA). The criterion for statistical significance is $P < 0.05$.

REFERENCES

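### Polyp size is assigned an ordinary Wilcoxon rank sum test with no stated unit of analysis; if polyps are pooled, within-patient correlation is ignored and p-values are too small

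*Combined protocol and SAP*

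**What the plan says.** The Statistical analysis section assigns t tests to continuous factors, chi-square tests to categorical ones, and "Wilcoxon rank sum tests for ordinal variables (such as polyp size") to the rest. Polyp size is its only example of an ordinal variable. The sentence ends by giving the purpose of all these tests: "to assess differences in demographic and clinical characteristics of patients in each group".

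Three other places bear on the unit:

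- **Procedure:** "Polyp size is determined by comparison with open colonoscopic biopsy forceps pushed against the polyp". This is a measurement on one lesion.
- **Definition:** the three size classes also belong to a single lesion, for example "Small polyp is defined for polyp with size 6-9mm". No largest, mean or index polyp per patient is defined. The same section expects several lesions in some patients: "ADR-Plus is defined as the mean number of adenomas detected after the first adenoma in procedures in which at least one adenoma is found".
- **Intervention and randomization:** "Patients will be randomly assigned by a research assistant, by using a computer-generated randomization sequence". The patient is the randomised unit.

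No mixed model, GEE, clustered rank test or other allowance for several polyps in one patient appears anywhere.

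**The concern.** A rank sum test assumes that every value in the two samples is independent. The only size variable the plan defines can take several values in one patient. If sizes within a patient are positively correlated, a pooled data set holds less information than its polyp count suggests. The test's variance is then too small, and it rejects too often.

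What is at stake is interpretation. The Introduction places the controversy in polyps under 10 mm, and under Procedure only those are removed on insertion. If insertion inspection raises detection, readers will ask whether the extra lesions are mainly diminutive. A between-group size comparison is the obvious place to look, and the plan's only criterion for it is P < 0.05.

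**Working it through.** **1. The plan's own figure.** The documents give no design figure for polyp size. The one they do give is for ADR: 40% against 55%, two-sided 5%, 85% power.

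- Without continuity correction: n' = [1.960·√(2·0.475·0.525) + 1.036·√(0.40·0.60 + 0.55·0.45)]² / 0.15² = 197.5, so 198.
- With continuity correction: n = (n'/4)·[1 + √(1 + 4/(n'·0.15))]² = 210.6, so 211, as stated.
- 211 × 1.10 = 232.1, which gives 232 per group and 464 in total.

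ADR is one yes/no result per colonoscopy, so nothing below alters these numbers.

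**2. Assumed inputs.** The documents give neither the number of polyps per polyp-positive patient (m) nor the within-patient correlation of size (ρ). Both are assumptions, shown as ranges.

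**3. Approximation.** The design effect is DE = 1 + (m − 1)ρ, and the actual two-sided error is 2[1 − Φ(1.96/√DE)]. For example, m = 2 and ρ = 0.2 give DE = 1.2, 1.96/√1.2 = 1.789, and an error of 7.4%.

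| Mean polyps m | ρ = 0 | ρ = 0.1 | ρ = 0.2 | ρ = 0.3 | ρ = 0.4 |
|---|---|---|---|---|---|
| 1.5 | 5.0% | 5.6% | 6.2% | 6.8% | 7.4% |
| 2 | 5.0% | 6.2% | 7.4% | 8.6% | 9.8% |
| 3 | 5.0% | 7.4% | 9.8% | 12.1% | 14.4% |

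**4. Simulation with no true difference.** The setting was 211 patients per arm, half with a polyp, and size classes of 70/20/10% cut from a latent normal variable with within-patient correlation ρ. The test was a tie-corrected Wilcoxon on pooled polyps, with 8,000 runs per cell.

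| Polyps per positive patient | ρ = 0 | ρ = 0.1 | ρ = 0.2 | ρ = 0.3 | ρ = 0.5 |
|---|---|---|---|---|---|
| Mean 1.5, Poisson extras | 5.0% | 6.0% | 6.4% | 7.0% | 8.6% |
| Mean 2, Poisson extras | 4.8% | 6.2% | 7.0% | 7.7% | 10.5% |
| Mean 2, overdispersed | 5.0% | 6.3% | 8.1% | 9.3% | 13.0% |
| Mean 3, overdispersed | 5.0% | 8.4% | 11.2% | 14.4% | 19.7% |

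Further runs over ρ = 0.1-0.4 gave 5.4-17.5% at means of 1.5-3. Overdispersed counts exceed the approximation because a few patients then supply many polyps. With one polyp per patient, the error is about 5% whatever ρ is.

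**5. A patient-clustered analysis.** With 65/25/10% size classes, means of 2-3 and ρ = 0.1-0.4, a cluster-robust rank comparison held the error at 5.1-5.9%.

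**6. Largest polyp per patient as the alternative.** When both arms find equally many polyps, this summary is valid: the error was 4.6-5.4% in every setting of step 4. The intervention, however, is meant to find more polyps. With identical size distributions in both arms (overdispersed counts, ρ = 0.1-0.4, 3,000 runs per setting), the test on the largest polyp declared a difference in:

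- 7% of trials at 2.0 against 2.3 polyps per positive patient
- 9-12% at 2.0 against 2.5
- 20-32% at 2.0 against 3.0

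A separate run over the same contrasts gave 7-27%. The cluster-robust comparison stayed at 4.7-6.4%.

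**The case against.** The strongest objection comes from the same sentence, which says the tests compare characteristics of patients. The patient is the only unit the statistical text names. With one value per patient the ordinary Wilcoxon test is valid, and no passage says polyps will be pooled. A reader might infer that the plan commits to an invalid test. The documents do not support that, so the point has to stay conditional. The objection does not remove it, though. A per-patient analysis needs a summary rule that the plan does not contain, and the most obvious one, the largest polyp, responds to how many polyps are found as well as to how large they are.

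It can also be said that polyp size is not among the outcomes in the primary or secondary aim. The analysis text mentions it only as an example, and the documents never call a shift toward diminutive lesions a key finding. That is correct, and it limits the weight of the point. A reader might further infer that the main result is at risk. It is not: the section states "The primary aim of the study is to evaluate whether there is a difference in the ADR between the two study groups", and ADR is a per-patient outcome.

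Finally, clustering corrects the standard error but not selection. Any size comparison is confined to detected polyps, and detection is what the intervention changes. This stands, and the report should say so.

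**Conclusion.** The point holds in conditional form and is minor. The plan does not state the unit for polyp size. If polyps are pooled, the named test overstates significance whenever sizes within a patient are positively correlated and some patients have more than one polyp. For ρ = 0.1-0.4, the real error at a nominal 5% is about 5-9% at a mean of 1.5 polyps per positive patient and about 6-17% at a mean of 2-3. The upper end needs about three polyps per positive patient, overdispersed counts and a correlation near 0.4 together. The documents fix none of these inputs, so the figures show what is plausible and do not predict this trial's error rate. The consequence is confined to polyp size and any other comparison made polyp by polyp.

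**What to change.** In the Statistical analysis section, take polyp size out of the Wilcoxon example and add a sentence to this effect: size class (diminutive, small, large) is compared with the polyp as the unit of observation and the patient as the cluster, by a cumulative-logit GEE with independence working correlation and robust standard errors, or by a clustered rank sum test. Choose one of the two in advance. Apply the same rule to any other per-polyp comparison. If the largest polyp per patient is reported, present it as a supplement and not as the only size summary. Add that the comparison describes detected polyps only.

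The cost is one or two sentences and a few lines of SAS (PROC GENMOD fits the GEE). No new data are needed and the sample size does not change. The downside is somewhat less favourable p-values for per-polyp comparisons.
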